6.4 Handling of Culture Data from Central and Local Laboratory

Culture data from both central lab (IHMA) and local lab at Baseline (no post-baseline for central lab) will be handled as outlined below:

- All the culture results from central and local labs are merged by subject id.
- Final pathogen, susceptibility (to Ciprofloxacin) and extended-spectrum beta-lactamases (ESBL) status at baseline will be determined in the following order as follows,
 - 1. For all uropathogen (Appendix 3) central records with concentration of $\geq 10^5$ CFU/mL then central lab pathogen, susceptibility and ESBL (ceftriaxone > 1 as positive) status is considered as final results.
 - 2. For all other central lab records with concentration $< 10^5$ CFU/mL or contaminated sample or 'no growth', if their local lab records have a uropathogen with concentration of $\ge 10^5$ CFU/mL then local pathogen, susceptibility and ESBL status is considered as final results.
 - 3. If both statement 1 and statement 2 do not apply, then central results are considered as final results.

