Appendix 2 Microbiology

Method of Collection of Urine Specimens:

To obtain a clean catch sample of urine from a female patient, a thorough cleansing of the periurethral area is essential before specimen collection. Wash the area with a disinfectant and make all efforts to avoid any contact until urination is complete.

All patients should void the first part of the specimen into the toilet, then collect the remainder of the specimen in a sterile container.

Culture and Susceptibility testing

All gram-negative pathogens will be tested locally for antimicrobial susceptibility, as appropriate.

.

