4.4 Micro-MITT (m-MITT)

All MITT patients with a positive study entry urine culture defined as $\geq 10^5$ CFU/mL of a uropathogen and no more than 2 species of microorganisms identified in the study entry urine culture, regardless of colony count.

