4.7 Determination of Inclusion in Analysis Populations

Inclusion into the ITT, MITT, m-MITT and Safety populations will be determined programmatically from the electronic case report form (e-CRF) data. Inclusion into the CE populations will be determined programmatically from the e-CRF data and through a manual review conducted by the sponsor. The sponsor will review both clinical and microbiological data for determination of criteria used to assess inclusion in the CE populations and for determination of baseline and post-baseline pathogens. The sponsor will review the data concurrent with the conduct of the study. Inclusion into the ME populations will be determined programmatically.

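### SAP 6.4 lets an absent central record, or a central non-uropathogen at ≥10^5 CFU/mL, take precedence over a qualifying local uropathogen, although the same local culture overrides a central no-growth result

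*SAP*

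**What the plan says.** SAP 6.4 combines baseline cultures from a central and a local laboratory: "All the culture results from central and local labs are merged by subject id". It then applies three rules in order.

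- **Rule 1.** If the central laboratory has a uropathogen at ≥10^5 CFU/mL, "then central lab pathogen, susceptibility and ESBL (ceftriaxone > 1 as positive) status is considered as final results".
- **Rule 2.** This opens "For all other central lab records with concentration" and covers central records that are below 10^5, contaminated or without growth. If the local record then shows a uropathogen at ≥10^5, "then local pathogen, susceptibility and ESBL status is considered as final results".
- **Rule 3.** "If both statement 1 and statement 2 do not apply, then central results are considered as final results".

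SAP 4.4 defines the primary population as "All MITT patients with a positive study entry urine culture defined as" ≥10^5 CFU/mL of a uropathogen, with at most two species. It names no laboratory and does not refer to 6.4. SAP 4.7 adds: "Inclusion into the ITT, MITT, m-MITT and Safety populations will be determined programmatically", from e-CRF data. Protocol Appendix 2 describes local work only: "All gram-negative pathogens will be tested locally for antimicrobial susceptibility, as appropriate".

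**The concern.** Rule 2 is the only route by which a local culture can count, and it is written for central records that exist and fall into one of three named categories. Anything outside those categories goes to rule 3, which looks only at the central laboratory. A lost or never-sent central sample is therefore handled less favourably than a central sample that grew nothing, although the local evidence is identical. The same applies when the central laboratory reports an organism that SAP Appendix 3 never counts as a pathogen, such as Group B Streptococci, at ≥10^5.

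Three results depend on this assignment: who is in the m-MITT, who falls into the susceptible and non-susceptible groups, and the secondary dipstick outcome (SAP 5.2), which is itself the percentage with a positive baseline culture.

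**Working it through.** **Step 1. Apply the rules literally.** Take a woman whose local record shows a uropathogen at ≥10^5 CFU/mL and vary the central result:

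| Central result | Rule reached | Final result |
|---|---|---|
| Uropathogen ≥10^5 | 1 | central uropathogen |
| Below 10^5 | 2 | local uropathogen |
| Contaminated | 2 | local uropathogen |
| No growth | 2 | local uropathogen |
| Non-uropathogen ≥10^5, not reported as contaminated | 3 | central non-uropathogen |
| No record | 3 | central result, which does not exist |

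The last two rows are the problem. The fifth gives a definite result that ignores a qualifying local uropathogen. The sixth gives an undefined one. With no central record and a negative local culture, rule 3 again returns an empty result.

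**Step 2. Look for a repair elsewhere in the SAP.**

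- 4.4 could keep the woman in the m-MITT on her local culture, but her susceptibility under 6.4 would still be blank.
- 6.5 leaves other missing values missing and reduces denominators. It does not direct use of the local result.
- 7.1 describes its residual group as no pathogen or a contaminated sample, which fits neither case.
- 4.7 has the sponsor review baseline pathogens during the study but gives no rule for these cases.

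**Step 3. Planning counts (SAP 6.1).** Expected culture-positive: 250 − 50 = 200, or 200/250 = 80%. Expected non-susceptible: 40, or 40/200 = 20% of the positives. The plan gives no power calculation and no figure for missing central records, so there is no figure of its own to reproduce here.

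**Step 4. Illustrative size for the no-record case.** Let f be the share of the 200 positives without a central record who are then dropped, equally across susceptibility groups. Every value of f is an assumption.

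- m-MITT = 200(1 − f)
- Non-susceptible = 40(1 − f)
- Dipstick percentage, dropped women kept in the denominator as negative = 200(1 − f)/250
- Dipstick percentage, dropped women removed = 200(1 − f)/(250 − 200f)

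| f | m-MITT | Non-susceptible | Dipstick, kept | Dipstick, removed |
|---|---|---|---|---|
| 0 | 200 | 40 | 80% | 80% |
| 5% | 190 | 38 | 190/250 = 76% | 190/240 = 79.2% |
| 10% | 180 | 36 | 180/250 = 72% | 180/230 = 78.3% |
| 20% | 160 | 32 | 160/250 = 64% | 160/210 = 76.2% |

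**Step 5. Precision.** The SAP plans no confidence intervals, so this is only a yardstick: half-width = 1.96 × √(p(1 − p)/n). At an assumed response of 80%, it is 5.5 points for n = 200, 5.8 for n = 180 and 6.2 for n = 160. In the non-susceptible group at an assumed 50%, it is 15.5 points for n = 40, 16.3 for n = 36 and 17.3 for n = 32.

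**The case against.** The strongest reply is that 6.4 was written to reconcile two available results and is merely silent on an absent one. 4.4 asks for a positive culture from any laboratory, 4.7 works from e-CRF data with sponsor review, and the listings in 7.1 and 7.3 would show exclusions and isolates. On this view a one-line clarification is enough. Preferring a central non-uropathogen could also be a deliberate central-first hierarchy.

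Part of this stands. A reader might infer that a woman without a central record is declared free of pathogen and leaves the m-MITT. The SAP does not say so: her result is undefined, and 4.4 could keep her in. A reader might also infer from Protocol Appendix 2 that missing central records are likely. Its silence on a central laboratory shows no such thing, and no rate is given.

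The rest does not stand. Rule 3 is a stated catch-all, so this is more than missing detail, and for the central non-uropathogen it gives a definite result. A strict central-first hierarchy would not let rule 2 override a central no-growth result. Listings would reveal a problem but not resolve it. Resolving cases in sponsor review during an open-label study would bring judgement into baseline classification at a time when outcomes may be known.

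**Conclusion.** The point holds as a defect in the decision rule that should be corrected. Followed literally, rule 3 leaves one group of women without a final pathogen or susceptibility result and gives another group a non-uropathogen despite a qualifying local culture.

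Its size is unknown. The step 4 figures assume the missing rates and assume that the women are dropped; the documents support neither. For the primary response rate, no bias is shown if records are missing for logistic reasons, only a modest loss of precision. The dipstick percentage is more exposed, because at an assumed 10% it is 72% or 78.3% against 80%, depending on a denominator choice the plan does not settle.

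A reader might take 76%, 72% and 64% as the expected effect. They apply only if culture-positive women alone lack central records and all stay in the denominator as negatives. If instead 20% of all 250 women lacked a central record, whatever their culture result, and were left out, the percentage would be 160/200 = 80%, unchanged. The analysis is descriptive (SAP 7.6), so no hypothesis test is affected.

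**What to change.** Amend SAP 6.4 as follows:

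1. **Rule 2:** the local result is final when the local record has a uropathogen at ≥10^5 CFU/mL and either no central record exists or the central record is, for any reason, not a uropathogen at ≥10^5.
2. **Rule 3:** limit it to women with no qualifying uropathogen in either laboratory. Use the central result, or the local result if there is no central record.
3. **Missing local susceptibility:** keep women with a qualifying local uropathogen in the m-MITT, subject to the organism limits in SAP Appendix 3, in a separate group labelled susceptibility unknown.
4. **Links and reporting:** refer to 6.4 from 4.4, and tabulate m-MITT women by the laboratory that supplied the final result.

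The cost is SAP wording and one table, using data already planned. There is a small downside: more classifications rest on local results, which may be less complete. Protocol Appendix 2 provides local susceptibility testing for gram-negative pathogens as appropriate, while the m-MITT also admits *S. saprophyticus*. The ESBL threshold in 6.4 is stated only under the central rule. The source table lets a reader judge how much this matters.

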6.5 Handling of Missing Data

Missing data will be handled as outlined below: Confidential Page 12

 All missing and partial dates for events and assessments occurring after start of enrollment or for medications received after start of enrollment will be queried for a value. If no value can be obtained, substitutions will be made as follows:

- For start dates, missing months and days will be defined by "01", as long as this occurs on or after the first dose of study drug. If the algorithm produces a date prior to the first dose of study drug, the date of the first dose of study drug will be used for the partial date. For stop dates, missing months will be defined as "12" and days will be defined by the last day of the respective month. These substitutions will be used in calculations; however, the actual value recorded on the e-CRF will be used for all listings.
- The intensity and causality assessment for an AE cannot be missing. Missing data will be queried for a value. If no value can be obtained, worst possible scenario will be considered. For example, missing intensity will be considered as 'severe' and missing causality will be considered as 'treatment related'.

For efficacy response, missing data will be handled as follows:

- For any outcome measure,
 - Patients will be defined as an indeterminate at any outcome measure (overall or clinical or microbiological) if any data needed to determine the outcome of a patient is missing. For example, if the assessment of the symptoms was not completed at EOT, for any reason, the patient will be considered an indeterminate response. By definition, patients with an indeterminate response are included in the denominator for analyses in the ITT and m-mITT populations, and are considered failures.
- For the Investigator's assessment of clinical response at EOT and TOC
 - Patients will be considered an indeterminate response if data are not available for the evaluation of efficacy at EOT and TOC for any reason.
- Except as specifically noted for preplanned imputation analyses, missing values for other individual data points (not described above) will remain as missing. Missing values will not be imputed and only observed values will be used in data analyses and presentations.
- Where individual data points are missing, categorical data will be summarized based on reduced denominators (i.e., only patients with available data will be included in the denominators).

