8.2 Reporting Period

Adverse events will be collected from the time that the patient provides informed consent through TOC.

For SAEs, the reporting period to Iterum Therapeutics begins from the time that the patient signed informed consent, which may be prior to the patient's participation in the study, i.e., prior to undergoing any study-related procedure through the TOC. Any SAE occurring any time after the reporting period must be promptly reported if a causal relationship to investigational product is suspected

All AEs should be recorded on the CRF if they occur from the time the patient provides informed consent through TOC.

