6.6 Comments on Statistical Analysis

The following general comments apply to all statistical analyses and data presentations:

- Summaries will include frequency and percentages for categorical data; frequency and median for ordinal data; and number, mean, standard deviation, and median, minimum and maximum for continuous data.
- Duration variables will be calculated using the general formula: (end date start date) +1 for end dates after first dose and (end date start date) for end dates before first dose.
- If the reported value of a clinical laboratory parameter cannot be used in a statistical summary table (e.g., a character string is reported for a parameter of the numerical type),

a coded value must be appropriately determined and used in the statistical analyses. In general, a value or lower and upper limit of normal range such as '<10' or ' \leq 5' will be treated as '10' or '5' respectively, and a value such as '>100' will be treated as '100'. However, the actual values as reported in the database will be presented in data listings.

- Individual patient listings of all data represented on the eCRFs will be provided to facilitate the investigation of tabulated values and to allow for the clinical review of all efficacy and safety parameters.
- Version 9.4 of SAS® statistical software package will be used to provide all summaries, listings, graphs, and statistical analyses.

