7.8 Safety Analyses

Safety analysis will be conducted in the safety population. Safety parameters include adverse events.

Verbatim descriptions of AEs will be coded using Version 21.0 or higher of MedDRA. Summary tables will be provided for all treatment-emergent AEs (TEAEs). An AE is defined as any untoward medical occurrence in a clinical investigation patient administered a product or medical device, unless the event is captured in the study endpoint, as defined below; the event need not necessarily have a causal relationship with the treatment or usage. ATEAE is any AE that newly appeared, increased in frequency, or worsened in severity following initiation of ciprofloxacin. In addition, all AEs (including non-TEAEs), serious TEAEs, and TEAEs leading to study drug discontinuation will be provided in listings containing patient number, verbatim term, MedDRA system organ class and preferred terms, seriousness flag, intensity, relationship to study drug, action taken and outcome.

An overall summary of AEs will include number of patients who experienced at least one AE of the following categories: any AE, any TEAE, any drug-related TEAE defined as possibly or probably related to study drug, any serious TEAE, any drug- related SAE, any SAE leading to death, any TEAE leading to premature discontinuation of study drug, and any SAE leading to premature study drug discontinuation.

The number and percentage of patients reporting a TEAE will be tabulated by system organ class and preferred term for all TEAEs and TEAEs through TOC. TEAEs through TOC will also be summarized separately by system organ class, preferred term, and intensity (mild, moderate, and severe); and by system organ class, preferred term, and relationship (unrelated or related to study drug). A table will provide all SAEs (through TOC) by system organ class and preferred term. For all analyses of TEAEs, if the same AE (based on preferred term) is reported for the same patient more than once, the AE is counted only once for that preferred term and at the highest intensity and strongest relationship to study drug.

Analysis of the distribution of the duration of each adverse event as well as an overall mean adverse event duration will be presented.

If an AE starts on the same day that dosing is initiated, and the start time of the AE is missing then the AE is considered TEAE.

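### An adverse-event stop date with a missing month becomes 31 December with no upper bound, and that date enters the planned mean AE duration

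*SAP*

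**What the plan says.** SAP 6.5 covers missing and partial dates of events, assessments and medications after enrollment starts. They are queried first; then "If no value can be obtained, substitutions will be made as follows". For the end of an event, "For stop dates, missing months will be defined as" 12, and the day is the last day of that month.

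Imputed start dates have a bound: "If the algorithm produces a date prior to the first dose of study drug, the date of the first dose of study drug will be" substituted. No corresponding bound is given for stop dates.

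The imputed values are not only for display: "These substitutions will be used in calculations; however, the actual value recorded on the e-CRF will be used for all listings".

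SAP 6.6 fixes how durations are computed: "Duration variables will be calculated using the general formula" of end date minus start date, plus 1 for end dates after first dose. SAP 7.8 then promises the result: "Analysis of the distribution of the duration of each adverse event as well as an overall mean adverse event duration will be presented".

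Protocol 8.2 gives the collection period: "Adverse events will be collected from the time that the patient provides informed consent through TOC". TOC is Day 12 ± 1, and the last scheduled contact is the Day 21 ± 3 telephone call (Protocol 6.3 and Appendix 1). Protocol 8.1 has the investigator follow every AE until it resolves or stabilizes.

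**The concern.** Scheduled contact ends at about three weeks, yet the rule can place the end of an AE many months later. The imputed length is then the number of days left in the calendar year at onset, which has nothing to do with the event. A mean is sensitive to one extreme value, so one failed query with a missing month could make the reported mean AE duration largely a product of the rule. Listings keep the recorded partial date while the table uses 31 December, so a reader cannot recompute the mean from the listing without applying the rule.

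**Working it through.** The documents state no AE count, no expected AE duration and no onset dates, so there is no plan figure to reproduce.

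**Inputs**
- Imputed stop for a missing month: 31 December of the recorded year (SAP 6.5). I take the recorded stop year to be the onset year; a stop in the following year would give a longer duration.
- Duration D = end − start + 1 (SAP 6.6).
- Number of AEs, n: assumed 12 to 125 (about 5% to 50% of 250 patients, one AE each).
- True mean AE duration, m: assumed 3 to 7 days.

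**Imputed duration, month missing**
- Onset 15 January: 351 days.
- Onset 15 March: 292 days.
- Onset 15 September: 108 days.
- Onset 15 December: 17 days.
- Average over onset spread evenly through the year: 183 days.

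**Effect of one such AE on the mean**

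New mean = ((n − 1) × m + D) / n, and the factor is the new mean divided by m. With n = 50 and m = 3:

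| Case | D (days) | New mean (days) | Factor |
|---|---|---|---|
| 15 January | 351 | (147 + 351)/50 = 9.96 | 3.32 |
| 15 March | 292 | (147 + 292)/50 = 8.78 | 2.93 |
| Average onset | 183 | (147 + 183)/50 = 6.60 | 2.20 |
| 15 September | 108 | (147 + 108)/50 = 5.10 | 1.70 |
| 15 December | 17 | (147 + 17)/50 = 3.28 | 1.09 |
| Day only missing, onset 2 March, ended in March | 30 | (147 + 30)/50 = 3.54 | 1.18 |

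For D = 292 and m = 3, other AE counts give (87 + 292)/30 = 12.6 days with 30 AEs and (297 + 292)/100 = 5.9 days with 100. With n = 50 and m = 7, the mean is (343 + 292)/50 = 12.7 days, a factor of 1.81.

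**Range over the assumptions (onset mid-January to mid-December)**
- Largest: n = 12, m = 3, D = 351. (33 + 351)/12 = 32 days, factor 10.7.
- Smallest: n = 125, m = 7, D = 17. (868 + 17)/125 = 7.08 days, factor 1.01.

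**When the mean at least triples**

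This needs n ≤ (D/m − 1)/2. For D = 292 and m = 3 that is 48 AEs or fewer; for D = 183 and m = 4, 22 or fewer; for D = 17 and m = 3, 2 or fewer.

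**Missing day only**

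D is at most 31 days for an AE that began and ended in the same month. Over the same n and m the factor is 1.03 to 1.78, the top value arising only with 12 AEs and a 3-day mean.

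**With an upper bound**

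Take an AE starting on Day 1, a last contact on Day 24 (the latest scheduled day for the call) and no later AE follow-up. D is then at most 24 days. With n = 50 and m = 3 the mean is (147 + 24)/50 = 3.42 days, a factor of 1.14 in place of 2.93 for the 15 March onset.

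**The case against.** **Queries come first, and a missing month should be rare.** This stands as a limit on frequency. With contacts at Day 3 or 4, Day 12 and Day 21, a stop date known only to the year is an unusual failure, and the documents give no rate for it. The rule exists for failed queries, however, and one case can be enough to move a mean.

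**The SAP already guards the reader.** SAP 6.6 plans the median, minimum and maximum for continuous data, and SAP 7.8 plans the distribution of durations. An outlier would be visible and the median would hardly move. That stands, but it does not correct the mean, which is the overall figure SAP 7.8 names.

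**Late imputation is conservative.** SAP 6.5 does take the worst case for missing AE intensity and causality. Those rules assign a category the event could have had; an unbounded stop date can assign a length that no contact supports.

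**Two stronger readings to avoid.** A reader might infer that any incomplete stop date triples the mean. The documents do not support this: the month must be missing, and the factor depends on an AE count, a mean duration and an onset date that they do not give. A reader might also infer that no AE can validly last longer than about 12 days. Protocol 8.2 limits when AEs are collected, whereas Protocol 8.1 follows them to resolution or stability, so longer durations are legitimate.

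**Conclusion.** The gap is real and minor. A missing stop month yields 31 December, nothing in the documents caps it or exempts AEs from it, and the value reaches the mean planned in SAP 7.8. Under the assumed 12 to 125 AEs, true mean of 3 to 7 days and a stop in the onset year, one such date multiplies the mean by about 1.01 to 10.7. A threefold rise is one point in that range, not a prediction. The defect that needs no assumption about AE numbers is that the imputed length is set by the calendar: 292 days or 17 days for the same event, depending on whether it began on 15 March or 15 December. AE incidence and all efficacy results are unaffected, and SAP 7.6 plans no hypothesis tests.

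**What to change.** In SAP 6.5, add that an imputed stop date may not be later than the patient's last recorded contact or last AE follow-up, whichever is later. Naming AE follow-up keeps the rule consistent with Protocol 8.1, which a bound at TOC would not.

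In SAP 7.8, report the number of AEs whose stop date was imputed. A mean from complete dates only may be added as a sensitivity summary. It should not replace the main one, because it would make the bound irrelevant to the mean and could drop the longer or unresolved AEs, biasing duration downward.

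The cost is SAP wording and one extra count. The small downside is that the bound may understate the duration of an AE that truly continued past the last contact; the reported count tells the reader how many AEs could be affected.
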